medicine. We have successfully developed the software for our clinicians to perform point of care randomization without interrupting patient care. Patient-Centered Outcomes Research Institute (PCORI) recently awarded our center ([name]) an award for a multi-state study on “comparative effectiveness of pain cognitive behavioral therapy and chronic pain self-management within the context of opioid reduction”. We are using CHOIR and the same point of care randomization tool for this study of over 1000 patients (<https://www.pcori.org/research-results/2017/comparative-effectiveness-pain-cognitive-behavioral-therapy-and-chronic-pain>). Similarly, American Society of Anesthesiologists Foundation for Anesthesia Education and Research awarded the principal investigator for another study using CHOIR for point-of-care randomization (comparative effectiveness of duloxetine and desipramine in patients with chronic pain).

(c) Approach:

Study Design: We are proposing to conduct a pragmatic randomized clinical trial to compare long-term effectiveness of two novel spinal cord stimulation waveforms: high frequency and burst. We are planning to study the superiority of high frequency spinal cord stimulation in improving pain and function, and superiority of burst spinal cord stimulation in improving depression and anxiety.

Patients: We will enroll chronic pain patients referring to Stanford Pain Management Center who meet the following inclusion and exclusion criteria:

Inclusion Criteria:

1. Adult English-speaking patient 18 years old or above
2. Persistent pain in lower back and/or leg for more than six months
3. Candidate for spinal cord stimulation (with either high frequency or burst waveforms) based on recommendations from Stanford Pain Management Center Neuromodulation Multidisciplinary Team Conference.

Exclusion Criteria:

1. Motor weakness in neurological examination in lower body based on the assessment by treating pain physicians
2. Previous failed spinal cord stimulation trial with either high frequency or burst waveforms
3. Patient refusal

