Randomization: After obtaining informed consent, the patients who meet the inclusion and exclusion criteria will be 1:1 randomized to undergoing treatment with spinal cord stimulation with either high frequency or burst waveforms. Treating pain physician will randomize the patient during clinic visit using CHOIR point-of-care randomization system. Randomization algorithm will be based on computer generated numbers in random blocks of four, six and eight.

Blinding: Two different competing manufacturing companies will be providing devices that deliver these two waveforms. Interacting with the manufacturer representative for programming and device maintenance will inform the patient of the type of waveform. Therefore, blinding will be challenging, and we will not attempt to blind the patients to the treatment they are receiving. The risk profile and maintenance of these devices are similar; they are novel to the patients with similar efficacy literature. Thus, we do not expect differences in either compliance or therapy expectation secondary to lack of blinding. The figure shows the process of the study up to randomization.

Intervention: At Stanford Pain Management Center, pain physicians identify candidates for spinal cord stimulation; thereafter, they refer these patients to our pain psychologists. A multidisciplinary neuromodulation team conference – which is attended by pain physicians and pain psychologists in our division – assesses appropriateness of spinal cord stimulation for these candidates based on their pain diagnosis, spinal anatomy, history of spine surgery, medical comorbidities, psychological comorbidities, expectations, cognitive status and mood stability. The team also recommends the choice of devices appropriate for each patient who is identified as an optimized candidate. With current evidence, the team does not distinguish between high frequency and burst waveforms. The checklist of items discussed during these team conferences is provided in Appendix 1. The treating physician will then obtain informed consent and randomize the patients who are identified as optimized candidates for spinal cord stimulation by multidisciplinary neuromodulation team conference. These participants will receive treatment with either high frequency or burst spinal cord stimulation.

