Primary Outcome:

- Change from baseline in pain intensity at 12 months. Baseline pain intensity is measured at last CHOIR completion before trial, and is based on patient reported outcome in CHOIR for average pain in the week prior to completion of questionnaire.

Secondary Outcomes:

1. Patient global impression of change at all follow up time points
2. Pain intensity at all follow up time points
3. Change from baseline in function at 12 months
4. Function at all follow up time points
5. Change from baseline in pain interference at 12 months
6. Pain Interference at all follow up time points
7. Change from baseline in depression at 12 months
8. Depression at all follow up time points
9. Change from baseline in anxiety at 12 months
10. Anxiety at all follow up time points
11. Daily opioid dose in morphine equivalent at all follow up time points

Analytic Plan: We will test the hypotheses that:

1. High frequency spinal cord stimulation is more effective than burst spinal cord stimulation in decreasing pain at 12 months in patients with chronic low back and/or leg pain.
2. High frequency spinal cord stimulation is more effective than burst spinal cord stimulation in improving pain, pain interference and function in patients with chronic low back and/or leg pain.

We will use repeated measure linear regression to compare these measures between the groups at follow up time points with time as the fixed effect and treatment as random effect. This method allows missing data subject to assumption of missing at random.

3. Burst spinal cord stimulation is more effective than high frequency spinal cord stimulation in improving depression and anxiety in patients with chronic low back and/or leg pain.

We will use repeated measure linear regression to compare these measures between the groups at follow up time points with time as the fixed effect and treatment as random effect. This method allows missing data subject to assumption of missing at random. Some improvement in depression and anxiety is expected to be the result of improvement in pain and function. We will also perform a stratified analysis in responders (patients who achieve >50% pain relief) and non-responders (patients who do not achieve 50% pain relief) to the treatments.

4. Patients receiving burst spinal cord stimulation will report higher satisfaction with treatment using patient global impression of change compared with patients receiving high frequency spinal cord stimulation.

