We will use SAS Enterprise Guide (SAS Institute Inc., Cary, NC) for all analyses. Our null hypotheses are similarity of measures. We will perform a two-sided hypothesis testing with accepted type I error of 0.05. We will compare baseline characteristics using t-test for continuous variables and chi-square for categorical variables. We will adjust for the variables that are different between the groups in our final regression model. Our primary analysis will be based on modified intention-to-treat. We will only exclude patients with no follow up data from our final analysis. We will then perform a secondary analysis based on implants only (excluding patients who do not achieve appropriate pain control in trial period).

We will then perform the following subgroup analyses:

1. Patients who have undergone lumbar spine fusion versus patients who have not.
2. Patients with back pain only (based on baseline body map) versus patients with back and leg pain or leg pain only.

3. Patients with PROMIS depression measure of above 90th percentile in baseline evaluation.
4. Patients with PROMIS anxiety measure of above 90th percentile in baseline evaluation.

The rate of CHOIR survey completion is more than 60% in our routine clinical care. We expect a higher rate for our proposed study considering that these surveys are abbreviated, and participants will receive more frequent reminders as well as telephone reminders (currently patients receive only one email reminder to complete the survey). For our primary outcome we will try to minimize missing data by calling the patients who do not complete the surveys up to seven times; we will try to ask and record the pain intensity even if they are not willing to complete surveys. Our analysis model will allow for missing data in longitudinal variables, subject to assumption of missing at random.

Data and Safety Monitoring Plan: We will not perform any interim analyses for benefit, harm or futility. We will establish a data and safety monitoring board consisting of investigators, at least two independent clinicians in our clinic (not part of the study team), and at least one neurosurgeon subspecialized in spine surgery who will monitor the study quarterly for adverse events and patient safety, reporting of adverse events, enrollment pace and study timeline, quality of data, and deviations from the protocol.

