Sample size: The highest standard deviation of NRS pain scale in our clinic is 2.25 based on prior publications.^{19,21-25} Accepting type I error of 0.05 with 80% power, we will require 80 participants per group to detect one unit between-group difference in change from baseline in NRS pain scale. We are proposing a more conservative (larger) sample size to preserve power considering that some patients do not proceed from trial to implant and do not receive therapy. Currently more than 80% of patients who undergo a trial of spinal cord stimulation proceed to receiving an implant. We will therefore target 100 patients in each arm. Correlation between repeated measure will decrease variance and increase the power of the proposed study.

Timeline: Stanford Pain Management Center performed more than 120 trial of spinal cord stimulation in 2017 and this practice is increasing in our division. We expect a high consent rate considering the nature of our study. We believe we will be able to complete recruitment in two years; thus, last follow up of last recruited patient will be completed by five years.

Data Management: CHOIR will be the main tool for data collection and storage for the study. At completion of the study, the data from CHOIR, participants' electronic health records and California Prescription Drug Monitoring Program will be downloaded for analysis. After initial steps of data preparation, we will de-identify the dataset for further analysis. The principal investigator will save the de-identification code on a secure computer within Stanford University Network only.

Limitations:

1. One of the most important advantages of pragmatic clinical trial with less stringent inclusion/exclusion criteria is to improve the ability to generalize the results to a wider range of patients. However, considering that the current study is a single center study conducted in a tertiary pain management center, our sample might not be representative of chronic pain patients seen by community pain providers.
2. Our aim is to integrate our trial into patient care; thus, we are not blinding the provider and the participants. Method of data collection is similar in both groups and does not involve interaction with investigators. This will minimize, but not eliminate, the bias introduced by proceeding with an open label design.

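### Hypotheses 2 to 4 are put up for testing with no deciding visit, order or adjustment, and hypothesis 2 tests pain a second time

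*Combined protocol and SAP*

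**What the plan says.** The Analytic Plan puts four hypotheses under one heading as hypotheses to be tested. Hypothesis 1 is pain at 12 months. Hypothesis 2 reads "High frequency spinal cord stimulation is more effective than burst spinal cord stimulation in improving pain, pain interference and function in patients" and names no visit. Hypothesis 3 favours burst on depression and anxiety. Hypothesis 4 favours burst on the patient global impression of change (PGIC) and gives neither a visit nor a method. The only error statement is "We will perform a two-sided hypothesis testing with accepted type I error of 0.05".

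For hypotheses 2 and 3 the method is a repeated-measures regression comparing the groups over the follow-up times. Data Collection sets seven of these: 1, 3, 6, 12, 18, 24 and 36 months. The secondary outcomes include "Pain intensity at all follow up time points". Function, pain interference, depression and anxiety each appear twice, as change at 12 months and as the measure at every follow-up.

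Study Design names two superiority objectives. One is high frequency for pain and function; the other is "superiority of burst spinal cord stimulation in improving depression and anxiety". Specific Aim 2, however, expects high frequency to do better on stress and anxiety.

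The plan does name one primary outcome, change in pain at 12 months. The sample size rests on that comparison, and no interim analysis is planned.

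**The concern.** For hypothesis 1 the reader knows which test decides the claim and what its error rate is. For hypotheses 2 to 4 the reader knows neither. The plan does not say which visit decides, whether the test is one overall treatment effect or a contrast at a visit, whether change or level is used, or how several results under one hypothesis combine. Nor does it call these hypotheses exploratory.

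Two claims are exposed. The burst claim on mood is a design objective with no primary endpoint behind it, so it would rest entirely on tests without error control. Pain has a second route: if month 12 is not significant, nothing in hypothesis 2 prevents a claim of high-frequency superiority from another visit. For anxiety, a result in either direction would match one of the plan's own stated hypotheses.

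**Working it through.** **1. The plan's own figure.** Inputs from Sample size and Randomization: "The highest standard deviation of NRS pain scale in our clinic is 2.25"; "Accepting type I error of 0.05 with 80% power"; a difference of 1 unit; patients "will be 1:1 randomized".

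n per group = 2 × (1.960 + 0.842)² × 2.25² / 1² = 2 × 7.85 × 5.0625 ≈ 79.5, so 80. This matches "we will require 80 participants per group to detect one unit between-group difference in change from baseline in NRS pain scale". Allowing for 20% not reaching implant, 80 / 0.80 = 100, the target per arm. The calculation is for a single test at 0.05, namely hypothesis 1.

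**2. Counting tests.** The six measures are pain, interference, function, depression, anxiety and PGIC. Five are not pain. With seven visits, the largest reading of the hypotheses is 6 × 7 = 42 tests, and 42 × 0.05 = 2.1 false positives are expected if there is no true difference.

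**3. One month-12 test for each of the five non-pain measures.** If the tests were independent, 1 − 0.95⁵ = 22.6%. The measures are correlated, but the documents give no correlations, so these are assumed. Null z-statistics were simulated from a multivariate normal distribution, counting trials with any |z| > 1.96.

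- Between-measure correlation 0.5 to 0.6: 17-18% two-sided.
- Counting only results in the hypothesised direction (0.025 per test): 8-9%.

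The directional figure treats all hypothesised directions as positively correlated. Hypothesis 2 favours high frequency, and hypotheses 3 and 4 favour burst. If pain and mood improve together, the correlation between those two groups of tests would be negative and the rate somewhat higher. It cannot exceed 5 × 0.025 = 12.5%. The two-sided figures do not depend on this assumption.

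**4. Every visit tested.** The correlation structure is exchangeable between measures and over time, with 0.5-0.6 between measures and 0.5-0.8 over time (assumed).

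| Event with no true difference | Rate |
|---|---|
| Any of 42 tests, two-sided | 47-69% |
| Any of 42 tests, hypothesised direction | 24-38% |
| Pain not significant at month 12, but favouring high frequency at another visit | 5-9% |

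For scale, hypothesis 1 alone favours high frequency by chance in 2.5% of null trials. Adding the second route gives roughly 2.5 + 5 = 7.5% to 2.5 + 9 = 11.5% for a false pain claim in that direction.

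**5. Sensitivity.** Over a wider grid (0 to 0.9 between measures, 0.3 to 0.9 over time), one test for each of all six measures gives about 11% to 26%. All 42 tests give about 23% at correlations of 0.9/0.9, and 1 − 0.95⁴² = 88.4% if independent. Every setting tried exceeds 5%.

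Not counted: daily opioid dose, the implants-only analysis, the responder strata and the four subgroup analyses.

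**The case against.** The strongest reply is that the plan already has a confirmatory structure: one primary outcome, a sample size built on it, no interim looks, and everything else labelled secondary. That stands. A reader might infer that the trial's stated 5% is broken. It is not: hypothesis 1 is one test, and the plan never describes 0.05 as a family-wise rate.

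A reader might also infer that 42 tests at 0.05 are planned. The documents do not say so. The model is described with time as a fixed effect and treatment as random, with no treatment-by-time term, so one treatment effect per measure is at least as natural a reading. The 42-test figures therefore describe the largest reading, not the stated analysis.

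Two-sided counting includes results against the hypothesis. That objection is fair for pain, function and interference, so directional rates are given as well. It is weaker for anxiety, where the plan states both directions.

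Finally, a reader might infer that clinicians will be told to choose a device on secondary results. The Background section says only that the findings should inform that choice.

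What the objection does not answer is that a secondary label is not a decision rule. Hypotheses 2 to 4 are still offered for testing at 0.05, and one of them carries a superiority objective.

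**Conclusion.** The point holds in limited form. The primary test is sound at 5%. Claims under hypotheses 2 to 4, and any pain claim made through hypothesis 2, have no error control because the deciding test is not named.

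On the modest reading of one month-12 test for each of five measures, the chance of at least one false significant result is about 17-18% two-sided, or 8-9% in the hypothesised direction. Testing every visit would raise this to 47-69% two-sided (24-38% directional). These figures rest on assumed correlations. The size varies with them, but inflation above 5% was present throughout the range tried for both six single tests and all 42. This should be settled before the data are analysed; it does not undermine the primary result.

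**What to change.** In the Analytic Plan:

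- State that the claim on pain rests only on hypothesis 1 at month 12, and remove pain from hypothesis 2.
- Let one month-12 contrast per measure decide hypotheses 2 to 4: function, interference, depression, anxiety and PGIC. Change at month 12 is already listed for the first four, so only PGIC needs a visit assigned.
- If superiority is to be claimed on these, apply Holm over the five or a fixed order. Otherwise label them exploratory.
- Report all other visits as differences with 95% confidence intervals and no superiority claim.
- Reconcile the direction for anxiety between Specific Aim 2 on one side and Study Design and hypothesis 3 on the other.

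Holm is one acceptable choice. Used beside a primary test at 0.05, it holds each family at 5%, so the two together are bounded by 5% + 5% = 10%. If 5% overall is wanted, place hypothesis 1 first in a fixed order. The price is that a burst claim on mood would then depend on the pain result.

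The cost is wording. Under Holm, the smallest of the five secondary p-values must be below 0.05 / 5 = 0.01. The sample size stays at 80 per group, target 100, because the primary test keeps its full 0.05. Splitting alpha over all six measures instead (0.05 / 6 = 0.0083) would need 123 per group and leave 69% power for pain at 100 per arm, so it is not recommended.

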The trial and implant process will be identical to high frequency with one difference: correct placement of the leads will be confirmed during the trial procedure by inducing paresthesia over the painful area (instead of standard anatomical placement with high frequency). The parameters of the stimulation are as below: each burst includes 5 pulses of electrical stimulation at intra-burst frequency of 500 hertz without time for discharge in between pulses. These bursts will be repeated at inter-burst frequency of 40-60 hertz. The amplitude will range between 0 and 15 milliamperes.

Data Collection: As a part of evaluation for spinal cord stimulation, patients in our clinic complete initial survey on Collaborative Health Outcomes Information Registry (CHOIR). The participants will receive electronic surveys via email at 1, 3, 6, 12, 18, 24 and 36 months after the operation for implant of spinal cord stimulator (or trial in case of failed trial). The participants will receive email reminders after three and five days if the surveys are not completed. If the participants do not complete the surveys within seven days of receipt of the survey link, they will be contacted to be reminded of the survey. These surveys will include average and worst Numerical Rating Scale (NRS) of pain; National Institute of Health (NIH) Patient Reported Outcomes Measurement Information System (PROMIS) measures for function, pain interference, depression and anxiety; patient global impression of change on a 7-point Likert scale; and questions about any adverse events related or unrelated to the therapy. Data about use of other analgesics and medications, and pain interventions

will also be recorded at these intervals from participants' electronic health records and California Prescription Drug Monitoring Program. We will also record participants' baseline characteristics including age, sex, main pain diagnosis, other pain diagnoses, psychological comorbidities, medical comorbidities, medication use, and education level.

Adverse events will be reported to the principal investigator either directly by the participants or through the treating pain physician at Stanford Pain management Center. The principal investigator is responsible for reporting the adverse events and deviations from the protocol appropriately to institutional review board and other authorities.

Mood instability will be monitored as a component of routine clinical care by treating physician.

Outcomes:

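### Covariates are picked by baseline significance tests, so baseline pain is not assured a place in the primary model; fixing it in advance gains power at no cost

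*Combined protocol and SAP*

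**What the plan says.** The primary outcome (Outcomes) is "Change from baseline in pain intensity at 12 months", using average pain over the preceding week and the last registry survey before the trial procedure as baseline. The Analytic Plan uses a repeated-measures linear regression to "compare these measures between the groups at follow up time points with time as the fixed effect and treatment as random effect". Time and treatment are the only terms named, here and in Specific Aim 1.

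Covariates are dealt with in two consecutive sentences of the Analytic Plan. The first reads "We will compare baseline characteristics using t-test for continuous variables and chi-square for categorical variables". The second reads "We will adjust for the variables that are different between the groups in our final regression model". No threshold for a difference is given; the only level stated nearby is the general one: "We will perform a two-sided hypothesis testing with accepted type I error of 0.05".

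Under Data Collection, the plan says: "We will also record participants' baseline characteristics including age, sex, main pain diagnosis, other pain diagnoses, psychological comorbidities, medical comorbidities, medication use, and education level". Baseline pain is collected but is not in that list. Under Randomization, allocation is 1:1 in random blocks with no stratification factor, so the design implies no covariate either.

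**The concern.** When allocation is random, a significant baseline difference between all randomised patients is a chance event. A rule that admits covariates on that ground selects on noise. What makes a covariate worth having is its relation to the outcome, and for change in pain the obvious candidate is baseline pain.

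Three things follow:

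- **Power.** Subtracting baseline fixes its coefficient at 1. Unless the correlation between baseline and follow-up is perfect, this leaves regression-to-the-mean noise that a fitted coefficient would remove.
- **Near-miss imbalance.** A baseline difference just short of the cut-off is left uncorrected, although it shifts the change-score comparison.
- **Pre-specification.** The form of the primary model is settled only after the arms have been compared, in an open-label trial, and without a stated cut-off.

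**Working it through.** **Inputs from the documents.** SD 2.25, described under Sample size as that of the NRS pain scale; 1-unit difference; two-sided 0.05; 80% power; 80 per group raised to 100 per arm; more than 80% of trialled patients go on to implant.

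**Assumed.** Baseline-to-12-month correlation r of 0.3, 0.5 or 0.7 (the documents give none), and a 0.05 cut-off for the baseline tests.

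**1. The plan's own figure.** The Sample size section says "Accepting type I error of 0.05 with 80% power, we will require 80 participants per group"; the target there is a 1-unit difference in NRS change. n = 2 × (1.960 + 0.842)² × 2.25² / 1² = 79.5, so 80 per group; 80 / (1 − 0.20) = 100. Both reproduce, with 2.25 used as the SD of change.

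**2. Gain from adjustment.** With equal SD s at both times:

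- SD of change = s√(2(1 − r))
- residual SD after adjusting for baseline = s√(1 − r²)
- variance ratio, adjusted to unadjusted = (1 + r)/2, which is 0.65, 0.75 and 0.85 at r = 0.3, 0.5 and 0.7

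The ratio is below 1 for every r below 1.

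**3. Reading 2.25 as the SD of change.** Adjusted residual SD = 2.25√((1 + r)/2) = 1.81, 1.95, 2.07. The required n per arm falls from 80 to 52, 60, 68. Simulated power with 100 per arm and a 1-unit difference (40,000 trials per setting):

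| r | Plan's rule | Always adjust |
|---|---|---|
| 0.3 | 89.2% | 97.2% |
| 0.5 | 88.6% | 94.9% |
| 0.7 | 88.5% | 92.3% |

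**4. Reading 2.25 as the SD of a single score.** The SD of change becomes 2.66, 2.25, 1.74; the adjusted SD becomes 2.15, 1.95, 1.61. At r = 0.3 and 100 per arm the standard errors are 2.66 × √(2/100) = 0.38 and 2.15 × √(2/100) = 0.30. For a 1-unit effect at r = 0.3, the normal approximation gives 75.7% unadjusted and 90.9% adjusted.

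If the 20% not implanted show no difference between arms, the effect is 1 × 0.80 = 0.8. Simulated power with 100 per arm (20,000 trials per setting):

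| r | Plain change score | Plan's rule | Always adjust |
|---|---|---|---|
| 0.3 | 56% | 57% | 75% |
| 0.5 | 71% | 72% | 82% |
| 0.7 | 90% | 90% | 94% |

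**5. Type I error.** Applied to baseline pain at 100 per arm, the rule gives 4.0% to 4.8% across both readings of the SD. It is slightly conservative.

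**6. Near-miss imbalance.** Suppose baseline pain differs by 1.9 standard errors, so it is not flagged. Under the null, the change-score z statistic then has mean 1.9√((1 − r)/2) in absolute value and SD √((1 + r)/2). At r = 0.3 these are 1.12 and 0.81, and the chance of exceeding 1.96 in absolute value is about 15%. At r = 0.5 and 0.7 it is about 12% and 9%. The adjusted analysis stays at 5%.

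**7. Irrelevant covariates.** If the eight listed characteristics were independent single tests at 0.05, at least one would be flagged by chance with probability 1 − 0.95⁸ = 34%.

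**The case against.** The strongest reply is that the rule itself costs no power: against a plain change score it is level or about a point better. That is correct. The gap arises because baseline pain is not pre-specified, and deleting the rule alone would recover nothing. The loss is therefore relative to always adjusting, and the fix needs both parts.

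Other points stand in part:

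- The 57% vs 75% comparison combines the lowest assumed correlation, the single-score reading of the SD and a diluted effect. On the plan's own use of 2.25 the gap is about 4 to 8 points, and power stays above 80% for the full 1-unit effect. Dilution is a separate sample-size matter.
- The rule does not inflate the overall error rate.
- The 5% entry rate depends on an unstated cut-off. Baseline pain may not be among the variables tested, in which case it would never enter, which is worse for the plan.
- The primary analysis drops patients with no follow-up data, so differences in that set need not be pure chance. Selecting covariates by significance is still no remedy for selective loss.
- The open-label point is modest, since the rule is written down and uses baseline data only. The missing cut-off still leaves discretion.
- The 34% treats multi-part items as single independent tests, and one irrelevant covariate among 200 patients costs little.
- The simulation compares two time points and does not fit the full repeated-measures model. That model would adjust for baseline implicitly if baseline were one of the modelled outcomes, but the plan describes comparison at follow-up times only.

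**Conclusion.** The concern holds. The text fixes no covariate, and chance imbalance is the only route by which baseline pain can enter the primary model as a covariate. Always adjusting has higher power in every setting examined: by about 4 to 8 points at 100 per arm if 2.25 is the SD of change and the effect is 1 unit, and by about 4 to 18 points if it is a single-score SD and the effect is 0.8. These sizes rest on assumed correlations of 0.3 to 0.7 and shrink as the correlation approaches 1.

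The stated 80 and 100 per arm are not wrong on their own inputs, so on that reading the loss is a forgone gain. If 2.25 is a single-score SD and r is below 0.5, the unadjusted analysis has less power than the sample-size calculation implies. There is no overall inflation of type I error. The further defects are the poor conditional behaviour under near-miss imbalance and a primary model that is not fixed in advance. This should be changed, though it does not invalidate the trial.

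**What to change.** - Delete the adjustment rule and the baseline significance tests. Present the baseline table descriptively.
- State that the primary model includes baseline average-pain NRS as a covariate, whatever the observed balance.
- Include the matching baseline score in each PROMIS model (function, pain interference, depression, anxiety).
- Optionally add a short fixed list of prognostic variables already collected, for example prior lumbar fusion and back-only versus leg pain, named before any comparison of the arms.
- Label any adjustment prompted by observed imbalance as a sensitivity analysis.

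The cost is a change of wording in the analysis plan. It needs no new data, patients or visits. Because the change score already requires a baseline value, adding baseline NRS as a covariate excludes no further patients, and it uses one degree of freedom.
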